Currently, the most reliable tool for diagnosing preload dependence is a dynamic test: passive leg raise (supine) or Trendelenburg (prone) with continuous cardiac output monitoring. A $\geq 10\%$ increase in cardiac output indicates preload dependence. Studies, including work by our team, confirm sensitivity and specificity $>85\%$. This test performs well to identify patient who are preload-dependent, and who are consequently at higher risk of preload-dependent hypotension. Yet, in preload-independent patients (i.e. those with a negative passive leg raising test, no validated predictive test exists for ultrafiltration-related hypotension in relation with their switch to a preload-dependent status.

Research Hypothesis

A 250 mL rapid ultrafiltration challenge (15 or 30 minutes) may help identify preload-independent patients at risk of becoming preload dependent during CRRT

Justification of Methodological Choices

- Sequential crossover design: each patient serves as their own control, limiting variability.
- Randomization of challenge order prevents bias.
- 250 mL volume chosen as it mimics passive leg raise (~300 mL).
- Two rates (15 vs. 30 minutes) tested to assess the effect of ultrafiltration kinetics and plasma refilling.

The PiCCO® Monitoring Device

The device combines transpulmonary thermodilution and pulse contour analysis for continuous cardiac output and displays advanced hemodynamic parameters (extravascular lung water, pulmonary vascular permeability index, global end-diastolic volume index).

Benefit/Risk Assessment

- Benefit: collective, through validation of a new predictive test.
- Risk: minimal, transient hemodynamic instability possible
- No additional invasive procedures required.

Expected Outcomes

A UF challenge may have higher diagnostic performance than the passive leg raising test to identify patients at the transition between preload independence and dependence. It is simple, dynamic, inexpensive, and potentially useful in guiding ultrafiltration in CRRT patients.

RESEARCH OBJECTIVES

Primary Objective

To evaluate the diagnostic performance of a rapid ultrafiltration challenge (250 mL over 15 or 30 minutes) in detecting preload dependence in preload independent critically ill patients treated with continuous renal replacement therapy.

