- Each patient undergoes 2 ultrafiltration challenges (15- and 30-minute, in randomized order)
- Total: 40 evaluable challenges

Randomization

- Randomized order determined by sealed envelope method
- Each patient serves as their own control

Blinding

- Not feasible given the study design

Co-interventions

Recommendation for not changing any of the following parameters, prescription or settings during the trial's interventions:

- Sedation
- Mechanical ventilation
- Vasopressor and inotrope support
- Fluid bolus therapy or transfusion

Study Procedures

1. Baseline data collection (demographics, clinical scores, renal data, hemodynamics)

2. Calibration of the monitoring device and pre-test postural maneuver (PLR or Trendelenburg) during 1 minute with collection of the relative change in continuous cardiac index
3. Ultrafiltration challenge: 250 mL over 15 or 30 minutes (randomized), by setting a UF flow of 1000 ml/h or 500 ml/h, respectively
4. Re-calibration of the monitoring device and post-test postural maneuver (reference standard, PLR or Trendelenburg) during 1 minute with collection of the relative change in continuous cardiac index
5. Repeat sequence for second challenge after a wash-out period of 24h (cross-over design)
6. Follow-up: monitoring for 8 hours post-test for instability

Data Collected

- Demographics: age, sex, weight, height
- Clinical: history, reason for ICU admission, severity scores (SAPS II, SOFA)
- Renal: CRRT indication and parameters
- Hemodynamics: CI, CVP, HR, MAP, PP, EVLW, PVPI, GEDVi (before/after each step), vasopressor dosage
- Ventilatory settings: VT, PEEP, FiO₂, arterial blood gas results
- Results of the pre and post-test postural maneuvers
- Any severe and non-severe adverse events

ENDPOINTS / EVALUATION CRITERIA

Primary Endpoint

The diagnostic performance of the rapid ultrafiltration challenge (pooled 15- and 30-minute tests).

- Performance assessed by the area under the ROC curve (AUC) of cardiac index variation.
- Reference: continuous cardiac index relative variation induced by the post-test postural maneuver performed after the challenge.

Secondary Endpoints

1. Respective diagnostic performance of the 15-minute and 30-minute challenges (ROC AUC).
2. Determination of the optimal threshold of cardiac index variation (Youden index) with sensitivity, specificity, PPV, and NPV.
3. Comparative performance of challenges (pooled and separate) versus the pre-test postural maneuver.

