4. Comparison of diagnostic performance between the 15-minute and 30-minute challenges ROC AUCs compared using DeLong's test.
5. Analysis of additional hemodynamic parameters: CVP, HR, MAP, Pulse pressure, EVLW, PVPI and GEDVi (absolute values and relative changes, correlated with cardiac index variation).

6. Incidence of hemodynamic instability within 8 hours post-test (tachycardia, hypotension, decreased CI, mottling).

Study duration

- Inclusion period: 18 months
- Maximum participation per patient: 72 hours
- Total study duration: 18 months + 3 days

Sample size

- 20 patients planned.
- Each undergoes 2 ultrafiltration challenges (15- and 30-minute, randomized).
- Total: 40 evaluable ultrafiltration challenges.

The sample size was chosen pragmatically, consistent with the pilot/exploratory nature of the study.

STUDY PROCEDURES AND CONDUCT

Overall Study Flow

1. Screening and Inclusion
 - Verify inclusion and exclusion criteria.
 - Provide information to patient or legally authorized representative; obtain consent in compliance with French law.
2. Baseline Assessment
 - Collect demographics and clinical data (age, sex, weight, height, SAPS II, SOFA, reason for ICU admission, history).
 - Record renal data (CRRT indication and parameters, time since CRRT initiation).
 - Baseline hemodynamic measurements: CI, CVP, HR, MAP, PP, EVLW, PVPI, GEDVi, vasopressor dosage
 - Mechanical ventilation settings
3. Randomization
 - Determine challenge sequence (15 vs 30 minutes) using sealed envelopes.
4. Pre-test postural maneuver
 - Passive leg raise (supine) or Trendelenburg (prone).
 - Record hemodynamic parameters before and during maneuver.
5. Ultrafiltration Challenge
 - Remove 250 mL with UF over 15 or 30 minutes.
 - Monitor CI and hemodynamic parameters continuously.
 - Record parameters at the end of challenge.
6. Post-test Postural Maneuver (Reference)
 - Repeat maneuver (PLR or Trendelenburg).
 - Record hemodynamic parameters before and during maneuver.
7. Follow-up
 - Any hemodynamic instability episodes occurring over the following 8h

8. Second Ultrafiltration Challenge

- After a 24h wash-out period, repeat procedure with the alternate duration (30 or 15 minutes).
- Same sequence: pre-test maneuver → challenge → post-test maneuver.

9. Follow-up

- Monitor for 8 hours post-challenges.
- Record any hemodynamic instability.

Data Management

- Data recorded in a secure **electronic case report form (eCRF)**.

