STATISTICAL ANALYSIS

General Principles

- Analyses performed using R software (latest version available).
- Two-sided significance level set at 0.05.
- 95% confidence intervals reported.
- Analyses conducted on the intention-to-treat and per-protocol population (patients with at least one evaluable ultrafiltration challenge).

Primary Analysis

- The primary endpoint is the diagnostic performance of the ultrafiltration challenge (15- and 30-minute tests pooled).
- Performance assessed by calculating the area under the ROC curve (AUC) of cardiac index variation compared with the post-test postural maneuver.
- AUC values will be reported with 95% confidence intervals.

Secondary Analyses

1. Diagnostic performance of the 15-minute and 30-minute ultrafiltration challenge alone (ROC AUC).
2. Determination of the optimal threshold of cardiac index variation (Youden index) defining preload dependence, with sensitivity, specificity, PPV, and NPV.
3. Comparative diagnostic performance of ultrafiltration challenges (pooled and separate) versus the pre-test postural maneuver, compared using the

respective ROC AUCs of 15-minute and 30-minute challenges using DeLong's test.

4. Analysis of additional hemodynamic parameters (CVP, HR, MAP, PP, EVLW, PVPI, GEDVi) in absolute values and relative changes from baseline, correlated with cardiac index variation using Pearson or Spearman correlation.
5. Description of the incidence of hemodynamic instability within 8 hours post-test, expressed as proportions with 95% confidence intervals.

Handling of Missing Data

- Missing data will not be imputed.
- Analyses will be based on available data.
- The extent and reasons for missing data will be described.

Interim Analysis

No interim analysis is planned.

QUALITY ASSURANCE, ETHICS, AND DATA MANAGEMENT

Regulatory and Ethical Aspects

- The study will be conducted in compliance with the Declaration of Helsinki (2013 version) and the principles of Good Clinical Practice (ICH E6 R2).
- The protocol, patient information, and consent form have been submitted to and approved by the CPP Sud-Est VI (Comité de Protection des Personnes).
- The study has been declared to the CNIL (Commission Nationale de l'Informatique et des Libertés) in accordance with French law and the General Data Protection Regulation (GDPR, EU 2016/679).

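### DeLong's test does not fit the 15- versus 30-minute AUC comparison: each challenge has its own reference result, so the paired form cannot be used and the unpaired form ignores the crossover

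*Combined protocol and SAP*

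**What the plan says.** - **Test.** The endpoint section (Secondary Endpoints, item 4) states: "Comparison of diagnostic performance between the 15-minute and 30-minute challenges ROC AUCs compared using DeLong"'s test. Under Statistical Analysis, item 3 of the Secondary Analyses combines the comparison against the pre-test maneuver with the "respective ROC AUCs of 15-minute and 30-minute challenges using DeLong"'s test. 15 versus 30 minutes has no analysis item of its own. The Summary also names DeLong, again without a variant.
- **Reference.** Study Procedures, item 4, places the reference after each challenge: "Re-calibration of the monitoring device and post-test postural maneuver (reference standard, PLR or Trendelenburg) during 1 minute". Item 5 adds: "Repeat sequence for second challenge after a wash-out period of 24h (cross-over design"). The Overall Study Flow confirms that everything is repeated for the second challenge: "Same sequence: pre-test maneuver → challenge → post-test maneuver". Each patient therefore has two reference results, one per duration.
- **Pairing.** The methodological justification gives the reason for the design: "Sequential crossover design: each patient serves as their own control, limiting variability".
- **Size.** "20 patients planned" and "Total: 40 evaluable ultrafiltration challenges", a number described as pragmatic. No expected AUC, prevalence, correlation or power is given.
- **Inference.** The General Principles set a two-sided 0.05 level with 95% intervals, and count a patient as evaluable with at least one evaluable challenge. Missing data are not imputed.

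The plan does not say how within-patient correlation enters this comparison, or what happens when a patient's two reference results differ.

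**The concern.** DeLong's test has two forms, and neither matches this comparison.

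The form for correlated curves assumes two scores on the same subjects and one shared truth. Here a patient may be preload-dependent after one challenge and not after the other. A day has passed, and the two rates were chosen precisely to study ultrafiltration kinetics and plasma refilling, so the plan itself allows duration to alter the post-test state.

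The form for independent curves accepts two sets of labels. It sets the covariance between the two AUCs to zero, which discards the within-patient information that the crossover was chosen to use.

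This is the only planned test of the randomised factor, duration. In a pilot, its confidence interval is the main product, and an interval that does not match the design misstates what 20 patients can show. An unnamed variant also leaves the choice to whoever runs the software.

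**Working it through.** **1. The plan's own figure.** 20 patients × 2 challenges = 40, as stated. That is 20 per duration, with the same 20 patients on both curves. No power or precision figure is given, so there is none to reproduce.

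**2. Is there a shared label?** The share of patients with discordant references is not in the documents, so I assume a prevalence of 30% or 50% and vary the latent correlation between a patient's two reference results.
- Correlation 0: expected discordant patients = 20 × 2 × p × (1 − p). This is 20 × 2 × 0.3 × 0.7 = 8.4, or 20 × 2 × 0.5 × 0.5 = 10.0.
- Correlation 0.9 (simulation): about 2.5 (prevalence 30%) to 2.9 (50%) of 20, with at least one discordant patient in about 93–96% of simulated trials.

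Even with a very stable status, a common label vector would rarely exist, so paired DeLong cannot be applied as the reference is defined.

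**3. What the unpaired form does.** Let D be the difference between the two AUCs, with variances V15 and V30 and covariance C.
- Correct: Var(D) = V15 + V30 − 2C.
- Unpaired DeLong: V15 + V30.

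With equal variances and correlation ρ between the two AUC estimates, the unpaired standard error is too large by the factor k = 1/√(1 − ρ). The nominal 5% test then has a true level of about 2Φ(−1.96k).

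| k | ρ = 1 − 1/k² | level |
|---|---|---|
| 1.00 | 0 | 5.0% |
| 1.08 | 0.14 | 3.4% |
| 1.45 | 0.52 | 0.4–0.5% |
| 1.50 | 0.56 | 0.3% |

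**4. Simulation.** Inputs: 20 patients, two occasions each, own label per occasion, true AUC 0.80 at both durations, prevalence 30% or 50%. Correlations of labels and scores between occasions ran from zero to strong. All inputs except n are assumptions.
- No correlation: unpaired standard error about right, type I error 4–5%.
- Strong correlation, one set of runs: unpaired 0.147–0.160 against a true SD of 0.101–0.111. The ratios are 0.147/0.101 = 1.46 and 0.160/0.111 = 1.44.
- Strong correlation, a second set (prevalence 50%, label correlation 0.9, score correlation 0.8): unpaired 0.151, patient-clustered 0.101, empirical SD 0.097. The ratios are 0.151/0.101 = 1.50 against the clustered value and 0.151/0.097 = 1.56 against the empirical SD. Unpaired type I error was 0.3%, in line with the formula.
- Power for AUC 0.70 versus 0.90 in that last setting: 18% unpaired, 45% clustered. Across all settings examined in that set, clustered power was 27–45%.

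**5. Calibration of the replacement.** The clustered variance sums, within each patient, the difference between the two curves' structural components, which restores the −2C term. Its mean standard error tracked the true SD. Type I error was 3–5% in one set of runs and 3.6–7.2% in another.

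**6. One label for both curves.** The plan does not propose this. If it were done with the first challenge's label, an AUC of 0.80 on the other curve would fall to about 0.71, 0.60 or 0.50 at label correlation 0.9, 0.5 or 0. Other assumptions give a smaller bias at 0.9 (a spurious difference of 0.03–0.04). The direction is stable; the size depends on the model.

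**The case against.** **The protocol already ties each reference to its own challenge.** This is correct. A reader might infer that the plan invites scoring both curves against one day's label, with the inflated false-positive rates that would follow. The documents do not support that reading: the reference is the maneuver after the challenge, and the whole sequence is repeated. Single-label scoring would depart from the definition. It deserves one sentence excluding it, because software for paired DeLong expects one outcome vector.

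**The unpaired test is conservative, not invalid.** This also stands. A reader might infer that any DeLong variant gives a misleading significant result. With own labels and positive correlation the error is on the safe side, and with little correlation it is negligible.

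**The replacement may be liberal at n = 20.** A rough check with a simpler patient-summed variance gave type I error of 6.8–8.8% at 20–30% prevalence with zero to moderate correlation, against 3.4–6.2% unpaired. A sequence-stratified percentile bootstrap gave 7–9% in 400 runs. Other runs of the clustered variance gave 3–5%, so the result depends on implementation. Mild miscalibration is possible and should be stated.

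**This is a secondary comparison in a small pilot.** True. Even with the right variance, power for a gap as wide as 0.70 versus 0.90 stays below 50%. That argues for reporting an estimate with an interval; it does not justify an interval that ignores the design.

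**Conclusion.** The point holds in a limited form. As the reference is defined, paired DeLong cannot be applied to 15 versus 30 minutes, and unpaired DeLong drops the within-patient covariance. Under the assumed inputs, the unpaired standard error is between about right and roughly 45–50% too large (56% against the empirical SD in one setting), and type I error runs from about 5% to 0.3–0.5%. The loss is material only when a patient's two occasions are strongly correlated, and the documents give no information on that correlation. Positive correlation is itself an assumption, though it is the one on which the crossover's claim to limit variability rests.

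The point does not show inflated false positives under the plan as written. It does not touch the primary pooled AUC. It does not apply to a single-duration challenge compared with its own pre-test maneuver, where both scores share one post-test label and paired DeLong is appropriate. The correction is worth making because it is cheap and this is the only planned test of duration.

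**What to change.** Give 15 versus 30 minutes its own item under Secondary Analyses, separate from the pre-test comparison, and state that:

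1. Each curve uses the reference result from its own challenge; one occasion's result is never applied to both curves.
2. The AUC difference has a patient-clustered (Obuchowski-type) variance, or a bootstrap that resamples whole patients within randomised sequence. Name one method before the data are analysed.
3. The result is reported mainly as an estimate with a 95% CI, with a note that either method may be mildly miscalibrated at n = 20.
4. A patient with one evaluable challenge contributes to that curve only.
5. Paired DeLong is kept for a single-duration challenge against its own pre-test maneuver. The pooled version of that comparison has two challenges per patient and also needs patient-level variance.

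The cost is a short paragraph in the analysis section and a few lines of R. No new data, visits or patients are needed.

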- Comparative diagnostic performance of ultrafiltration tests (pooled and separate) versus pre-test postural maneuver, and between tests (15 vs. 30 minutes).
- ROC AUC values compared using DeLong's method.
- Hemodynamic variables measured by cardiac output monitoring (CVP, HR, MAP, pulse pressure, EVLW, PVPI, GEDVi), analyzed as absolute values and changes from baseline, correlated with cardiac index variation.
- Incidence of hemodynamic instability (tachycardia, hypotension, decreased cardiac index, mottling) within 8 hours after the ultrafiltration test.

Target Population

Adult ICU patients (under mechanical ventilation and sedation) with acute kidney injury (KDIGO stage 3) requiring continuous renal replacement therapy initiated within the past 14 days.

Sample Size

N = 20 evaluable patients, each undergoing 2 tests → total of 40 rapid ultrafiltration challenges.

Study Duration

- Inclusion period: 18 months
- Maximum participation per patient: 72 hours
- Total study duration: 18 months + 3 days

Expected Outcomes

The current reference dynamic test (passive leg raise or Trendelenburg) remains imperfect in assessing tolerance to fluid removal during CRRT, with sensitivity <80%. The UF challenge may prove more sensitive, particularly in patients at the borderline between the ascending and plateau phases of the Frank-Starling curve. This simple, dynamic, low-cost test could help clinicians individualize ultrafiltration prescriptions, avoid deleterious hypotension, and rapidly integrate into clinical practice. Currently, no specific dynamic test exists to evaluate the safety and efficacy of fluid removal in this population.

GENERAL INFORMATION

Title: Diagnostic performance of a rapid ultrafiltration test to assess preload dependence in critically ill patients treated with continuous renal replacement therapy.

Project Identifiers and Update History

- Sponsor Code: 69HCL21_1250
- ClinicalTrials.gov registration number: NCT05214729
- CPP Sud-Est VI favorable opinion date: XX/XX/XXXX

Version History

Version	Date	Reason for Update
1	02/11/2021	Initial draft
2	16/03/2022	Comments from CPP

Sponsor

Identity: Hospices Civils de Lyon

[name]

[name] [name]

Signature of the protocol on behalf of the Sponsor:

[name], Director of Health Research

Hospices Civils de Lyon, Health Research Directorate,

Administrative Headquarters,

[name],

[name],

[name]

[contact]

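### The pooled primary AUC uses two challenges per patient, but the plan names no interval or comparison method that allows for the pairing

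*Combined protocol and SAP*

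**What the plan says.** The design gives two challenges per patient: "Each patient undergoes 2 ultrafiltration challenges (15- and 30-minute, in randomized order"), separated by a 24-hour wash-out (Study Procedures). The Sample size section has "20 patients planned" and "Total: 40 evaluable ultrafiltration challenges", and describes the number as pragmatic. Each challenge has its own change in cardiac index and its own post-test reference maneuver.

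The Primary Analysis merges both durations: "The primary endpoint is the diagnostic performance of the ultrafiltration challenge (15- and 30-minute tests pooled"). On uncertainty it says only "AUC values will be reported with 95% confidence intervals". General Principles adds "Two-sided significance level set at 0.05". For comparisons, the Summary's Secondary Endpoints say "ROC AUC values compared using DeLong's method". Secondary Analyses item 3 covers ultrafiltration challenges, pooled and separate, against the pre-test maneuver. Item 4 has other hemodynamic variables "correlated with cardiac index variation using Pearson or Spearman correlation".

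Nowhere in the text available is there a mention of clustering, repeated measures, patient-level resampling or a mixed model. A stretch of text between General Information and the discussion of dynamic tests was not available. The statistical section itself is complete.

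**The concern.** Justification of Methodological Choices defends the crossover on the ground that patients act as their own controls, which reduces variability. That gain exists only if a patient's two results are correlated. The design therefore relies on a correlation that the analysis does not mention.

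The DeLong variance assumes independent units. Applied to 40 rows, it counts 40 units where there are 20. With no power calculation and no target AUC, the confidence interval is the plan's only primary statement of uncertainty. An interval that is too narrow would make a 20-patient pilot look more precise than it is. The same applies to the pooled threshold, sensitivity, specificity and predictive values, and to the p-value of the pooled comparison with the pre-test maneuver.

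**Working it through.** **1. The plan's own figure.** 20 patients × 2 challenges = 40, as stated. The plan gives no power, AUC or interval width to reproduce.

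**2. Bounds on the interval width.** Hanley–McNeil variance for AUC = A with m positives and n negatives:

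Var = [A(1−A) + (m−1)(Q₁−A²) + (n−1)(Q₂−A²)] / (mn), with Q₁ = A/(2−A) and Q₂ = 2A²/(1+A).

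Assumed, not in the documents: A = 0.80 and 30% reference-positive. Then Q₁ = 0.6667, Q₂ = 0.7111 and A² = 0.64.

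- 40 independent challenges (m = 12, n = 28): (0.16 + 11×0.0267 + 27×0.0711)/336 = 0.00706; SE 0.084; 95% half-width 1.96 × 0.084 = 0.165.
- 20 independent units (m = 6, n = 14): (0.16 + 5×0.0267 + 13×0.0711)/84 = 0.0145; SE 0.120; half-width 0.236.

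With positive within-patient correlation the honest half-width should lie between these. If a patient's two results were identical, the SE would be too small by a factor of √2 = 1.41.

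**3. Where between the bounds.** Simulation with 20 patients × 2 challenges, a binormal index variable and 4,000 runs per setting. The correlation ρ is applied both to a latent reference response, cut to give 30% positives, and to the index reading given status. The two variances compared, using centred placement values of positives and negatives:

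- Ordinary DeLong: s²₁₀/m + s²₀₁/n.
- Obuchowski: I₁₀/[(I₁₀−1)m²]·Σc² + I₀₁/[(I₀₁−1)n²]·Σd² + 2K/[(K−1)mn]·Σcd. Here c and d are a patient's summed placement values, I₁₀ and I₀₁ are the numbers of patients with any positive or any negative result, and K = 20.

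The first three result columns assume AUC 0.80. The last two are the pooled DeLong comparison with the pre-test maneuver, with both AUCs 0.75 and independent errors given status.

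| ρ | True SE / ordinary SE | Coverage, ordinary | Coverage, clustered | Type I error, ordinary | Type I error, clustered |
|---|---|---|---|---|---|
| 0 | 1.00 | 90.7% | 90.0% | 6.8% | 7.5% |
| 0.3 | 1.03 | 88.5% | 88.2% | 6.6% | 6.7% |
| 0.5 | 1.05 | 88.3% | 88.7% | 7.7% | 6.6% |
| 0.8 | 1.20 | 82.7% | 86.5% | 12.4% | 6.8% |

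The Monte Carlo error of a type I rate near 6.8% is √(0.068×0.932/4000) = 0.4 points, so the rates at 0 to 0.5 are hardly distinguishable.

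**4. Sensitivity.** With 20% or 50% positives, the SE ratio is 1.00–1.01 at ρ = 0.3, 1.05–1.06 at 0.5 and 1.20 at 0.8. A separate simulation (AUC about 0.79, 30% positive) gave ratios of 1.00, 1.03, 1.14 and 1.28 at 0.3, 0.5, 0.7 and 0.9, with type I error 6.6%, 6.4%, 9.6% and 13.7%. A further bivariate-normal model gave about 8% at 0.5 for the SE shortfall, the top of the range quoted.

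**5. Reversal.** If every patient has one positive and one negative reference result (index correlation 0.5, AUC 0.80), the true SE is 0.79 of the ordinary SE. The ordinary interval is then too wide.

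**The case against.** - **A reader might infer that the plan specifies an ordinary interval.** It does not. It names no variance method, and a patient-level bootstrap would comply with its wording. What stands is that nothing directs the analyst away from DeLong on 40 rows, and DeLong is the only method named for AUC inference.
- **A reader might treat the narrow interval as established.** It is conditional. The protocol handles preload dependence as a changing state: it studies a transition, excludes dependence found within the preceding 2 hours, and separates challenges by 24 hours. The own-control rationale suggests some correlation, but nothing in the documents supports a value of 0.7 to 0.9. At 0.3 the effect is negligible, and discordant pairs reverse it.
- **A reader might blame all the under-coverage on clustering.** Coverage is already about 91% with independent data at 30% positives. The clustered variance reaches only 88.7% at correlation 0.5 and 86.5% at 0.8. A patient bootstrap gave 90–92% in a smaller check. Neither restores 95%.
- **A reader might infer that a primary p-value is invalid.** The primary analysis has no hypothesis test. The p-value point concerns the secondary pooled comparison. Item 4 does not say whether its correlations are pooled.
- **This is a pilot with no decision rule.** True, and pairing does not by itself bias the pooled AUC estimate. That lowers the severity. It does not justify leaving the interval's unit of analysis undefined.

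**Conclusion.** The concern holds in conditional form. The plan pools paired challenges and names no method that respects the pairing; that much is plain from the text. Whether the pooled interval would be too narrow, and by how much, depends on a within-patient correlation the documents do not give.

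Under the assumptions above, the effect on the primary interval is small up to a correlation of about 0.5 and material from about 0.7. The pooled comparison follows the same pattern, with type I error rising to 10–14% at 0.7–0.9. Uncertainty about the direction favours a patient-level method, because it adapts either way. A 40-row method is right only when the dependence has no net effect.

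The intervals for the separate 15- and 30-minute AUCs use one row per patient and need no clustering correction. Their comparison with each other does need attention: it involves the same patients with separate reference results. Unpaired DeLong ignores the pairing, and standard paired DeLong assumes one shared reference status. This should be fixed, but it does not invalidate the design.

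**What to change.** - For every pooled estimate (AUC, Youden threshold, sensitivity, specificity, PPV, NPV, comparison with the pre-test maneuver, and any pooled correlation), specify a bootstrap that resamples patients and keeps both challenges together. For the AUC and its comparisons, the Obuchowski clustered-ROC variance is an alternative.
- Use the same patient-level resampling for the 15- versus 30-minute comparison.
- Describe the sample as 20 independent patients contributing up to 40 correlated challenges.
- State that intervals remain approximate at this size, whichever method is used.

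The cost is SAP wording and a few lines of R, with no extra data or procedures. The downside is a somewhat wider interval if the correlation is high, and slightly more variable standard errors if it is low.
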